7.2.2 Administration

Appropriately trained personnel of the study site will provide instruction pertaining to IMG-7289 administration and supervise the administration of IMG-7289 on any day that it is taken in the clinic. With the exception of ITP Day 1, it is not required that IMG-7289 be taken in the clinic; this will be determined based on the patient's regular daily dosing time. When applicable, the date and time of each administration in the clinic will be recorded in the source notes.

CCI [REDACTED]

CCI [REDACTED]: Initial Treatment Period

In the ITP, all patients will be treated daily for 169 days. Dosing will begin on Day 1 at the starting dose (D_s) of 0.6 mg/kg/d IMG-7289, free base, for all patients. Details on the selection of and rationale for the starting dose and dosing schedule can be found in Section 3.6.

Through the use of dose titration, the dose of IMG-7289 will be adjusted for each patient to that dose that provides sufficient exposure to safely inhibit thrombopoiesis for a fraction of the dosing cycle (designated as the D_{pi}). Dose-titration, both upward and downward, is contingent on the hematology assessment and comparison of hematology values from the prior visit. **Up-titrations** may begin on ITP Day 28 and occur no more frequently than every 4 weeks from the previous up- or down-titration. **Down-titrations** can be made at any time in the best interest of the patient. CCI

[REDACTED]

[REDACTED]

[REDACTED]

[REDACTED]

CCI
[REDACTED]

Please consult the medical monitor regarding dose modifications of IMG-7289 should an adverse event (AE) requiring a dose reduction occur, and also for the management of clinically significant changes in platelets, neutrophil counts, or other hematologic parameters.

CCI

CCI

8.2 Management of Study Toxicities

Adverse event intensity will be evaluated using the National Cancer Institute (NCI) Common Terminology Criteria for Adverse Events (CTCAE) version 5, published 27 November 2017.

Dose-limiting toxicity and stopping rules are defined in Sections 8.2.2 and 8.2.3 below. Expected IMG-7289 toxicities based on non-clinical and clinical studies are reported in the latest available edition of the Investigator's Brochure.

CCI

CCI

8.2.2 Dose Limiting Toxicity (DLT)

DLT is defined as any one of the following AEs that occurs through Day 8 of the ITP and is considered by the Investigator to be possibly, probably or definitely related to IMG-7289:

- Any Grade 2 or above thrombocytopenia associated with clinically significant bleeding*
- Any Grade 3 or above thrombocytopenia;
- Any Grade 4 or 5 non-hematologic adverse event;
- Any Grade 3 or above non-hematologic adverse event with failure to recover to Grade 2 within 7 days of drug cessation, with the following exceptions:
 - nausea, vomiting or diarrhea that responds to standard medical care
 - aesthenia lasting less than 14 days
- Any Grade 3 electrolyte abnormality unrelated to the underlying malignancy (for example, hyperkalemia *is* related to thrombocytosis and would therefore not qualify as DLT) and persisting greater than 24 hours.

*Clinically significant bleeding is defined as an event that is life-threatening, cannot be controlled and/or results in hemodynamic instability.

Patients who experience DLT will have their dose adjusted downward if the Medical Monitor and Principal Investigator deem it safe for the patient to continue on IMG-7289. Any patient that experiences DLT that results in discontinuation of IMG-7289 therapy may begin alternative therapy within 24-48 hours of discontinuation if their physician deems this safe and appropriate regarding the resolution of the DLT.

Please consult the Medical Monitor for IMG-7289 dose modifications for the management of clinically significant changes in platelets, neutrophil counts, or other hematologic parameters.

CCI

Term	Protocol Meaning
Collect MPN-SAF	MPN-SAF is to be completed by the patient in their native language and in the format provided. The MPN-SAF will be completed during Screening (as close to Day -7 as possible), pre-Dose Day 1 and weekly from Day 7 through the EoS Visit. Ideally, the MPN-SAF will be completed at the same time and day each week for consistency. On visit days, the MPN-SAF should be completed prior to the study visit, and if the patient arrives without a completed MPN-SAF, then it will be completed during the visit and collected prior to the patient departing. Importantly, multiple MPN-SAF forms will need to be provided to the patient for completion between visits, during each 'off week'. Date of completion should be documented on each MPN-SAF completed.
Full Local Lab Assessment	Assessment consisting of the following test panels performed locally (see Section 10.1.1 for specific analytes required): 
 • Hematology with automated differential • Biochemistry • Serum pregnancy test for women of child-bearing potential (WOCBP); results to be reviewed prior to dosing, if applicable
Bone Marrow Sampling	CCI
Dosing Instructions	
 • Instruct patients to refer to their Dosing Card every day for details on IMG-7289 dosing and what to do if a dose is missed • Take their IMG-7289 in accordance with Section 7.2.2 • Handle any missed IMG-7289 doses as per Section 7.2.5 • Bring all medication to every clinic visit, including empty bottles
Administer IMG-7289	Administer IMG-7289 with a glass of water, instruct patient to continue to fast for at least 30 minutes, and, if dosed in clinic, record the exact time of dosing.
Adverse Events and Concomitant Medications	Use non-directive questions (i.e., "How are you feeling") to query patient re: any AEs that may have occurred. Also, inquire about medication changes since the last visit.

Note: If at any time additional clinical evaluation outside of the visit schedule is deemed necessary by the Investigator, then unscheduled visits should occur as appropriate.

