12. Current use of a prohibited medication (e.g., romiplostim) or expected to require any of these medications during treatment with the investigational drug.
13. Known immediate or delayed hypersensitivity reaction or idiosyncrasy to drugs chemically related to IMG-7289 or LSD1 inhibitors (i.e., monoamine oxidase inhibitors; MAOIs) that contraindicates their participation.
14. History of any illness/impairment of gastrointestinal (GI) function that might interfere with drug absorption (e.g., chronic diarrhea), confound the study results or pose an additional risk to the patient by participation in the study; patients with gastric bypass surgery.

15. Use of an investigational agent within less than 14 days, or the equivalent of at least 7 half-lives of that agent, whichever is the longer, prior to the study Day 1.
16. Females who are pregnant or breastfeeding or plan to become pregnant or breastfeed during the study.
17. A concurrent second active and non-stable malignancy (patients with a concurrent second active but stable malignancy, such as non-melanoma skin cancers, are eligible).

GUIDELINES: These guidelines are for use by the Investigator, study staff and patient to safeguard patient safety while maintaining data integrity.

1. In general, supportive care (transfusions, administration of anti-fungals, etc.) should be maintained in accordance with institutional policy.
2. Patients taking medications with the potential to induce or inhibit CYP_{3A4} or CYP_{2D6} should be monitored closely for potential effects of co-administration; particular attention should be given to anti-infectives in the azole class.
3. Cessation of IMG-7289 is invariably associated with a rebound in thrombopoiesis and platelet counts may easily exceed the baseline value. When IMG-7289 is discontinued, the platelet count should be monitored closely and an alternative cyto-reductive therapy to lower platelets should commence within 24-48 hours.

CCI

Management of Study Toxicities: Adverse event intensity will be evaluated using the National Cancer Institute (NCI) Common Terminology Criteria for Adverse Events (CTCAE) version 5, published 27 November 2017. Please refer to Section 8.2 for additional detail on management of study toxicities, including reduction of the starting dose based on dose limiting toxicity (DLT).

Definitions:

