Hematologic Toxicity: Hematologic values outside of the normal reference range are inherent features of MPNs and are expected effects of many therapeutic attempts to manage these diseases. The effects of IMG-7289 on normal myeloid hematopoiesis observed in non-clinical and clinical studies are expected; these are pharmacodynamic effects of LSD1 inhibition by IMG-7289, thus are not regarded as adverse. These events, with the exceptions below, will not be considered DLTs.

Dose limiting toxicity (DLT): Any one of the following AEs that occurs through Day 7 of the Initial Treatment Period and is considered by the Investigator to be possibly, probably or definitely related to IMG-7289:

- Any Grade 2 or above thrombocytopenia associated with clinically significant bleeding*
- Any Grade 3 or above thrombocytopenia;
- Any Grade 4 or 5 non-hematologic adverse event;
- Any Grade 3 or above non-hematologic adverse event with failure to recover to Grade 2 within 7 days of drug cessation, with the following exceptions:
 - nausea, vomiting or diarrhea that responds to standard medical care
 - aesthenia lasting less than 14 days
- Any Grade 3 electrolyte abnormality unrelated to the underlying malignancy (for example, hyperkalemia *is* related to thrombocytosis and would therefore not qualify as DLT) and persisting greater than 24 hours.

*Clinically significant bleeding is defined as an event that is life-threatening, cannot be controlled and/or results in hemodynamic instability.

Patients who experience a DLT may have their dose adjusted downward if the Medical Monitor and Principal Investigator (PI) deem it safe for the patient to continue on IMG-7289. Any patient that experiences DLT that results in discontinuation of IMG-7289 therapy may begin alternative cytoreductive therapy to lower platelets within 24-48 hours.

Please contact the Imago medical monitor to discuss IMG-7289 dose modifications for the management of clinically significant changes in platelets, neutrophil counts, or other hematologic parameters.

Stopping Rules:

IMG-7289 will be discontinued in the event of the following:

- Post DLT, the Medical Monitor and Principal Investigator deem it unsafe for the patient to continue on IMG-7289.
- Post dose reduction due to DLT, the patient fails to demonstrate significant improvement within 21 days.

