10.1.1 Local Laboratory Measures

Biochemistry: Serum creatinine, uric acid, urea* or blood urea nitrogen (BUN)*, albumin, total bilirubin, gamma glutamyltransferase (GGT), alkaline phosphatase (ALP), alanine aminotransferase (ALT), aspartate transaminase (AST), lactate dehydrogenase (LDH), C-reactive protein (CRP) and serum ferritin.

Hematology: Hemoglobin, red blood cell count (RBC) (including nucleated RBC), hematocrit, platelets, white cell count and automated assessment of neutrophils, lymphocytes, monocytes, reticulocytes and blasts.

Coagulation: Prothrombin time (PT)*, activated partial thromboplastin time (aPTT) and International normalized ratio (INR).

Serum Pregnancy Test: For WOCBP, a serum pregnancy test will be utilized according to institution standard procedure. The result must be confirmed prior to next scheduled dose of IMG-7289.

[figure not shown]
Urinalysis: Leucocyte esterase, nitrites, urobilinogen, protein, pH, blood, specific gravity, ketones, bilirubin and glucose.

CCI [REDACTED]

Additional Tests for Italy: HIV test, HAV, HBsAg, HBsAb, HBcAb, HCV

CCI [REDACTED]

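### The DLT window ends on Day 7 in the protocol synopsis but on Day 8 in Section 8.2.2, and no visible SAP text settles which applies

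*Protocol*

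**What the plan says.** The protocol defines dose-limiting toxicity twice. The synopsis counts "Any one of the following AEs that occurs through Day 7 of the Initial Treatment Period". Section 8.2.2 reads: "DLT is defined as any one of the following AEs that occurs through Day 8 of the ITP". Both definitions require at least a possible relation to study drug in the Investigator's judgment, and both list the same events.

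The two places are cross-linked. The synopsis tells the reader: "Please refer to Section 8.2 for additional detail on management of study toxicities". Section 8.2 then says: "Dose-limiting toxicity and stopping rules are defined in Sections 8.2.2 and 8.2.3 below".

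They also differ on the consequence of a DLT. The synopsis has "Patients who experience a DLT may have their dose adjusted downward", and Section 8.2.2 has "Patients who experience DLT will have their dose adjusted downward". Both make this conditional on the Medical Monitor and the Principal Investigator judging continuation safe.

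Both lists include this criterion: "Any Grade 3 electrolyte abnormality unrelated to the underlying malignancy", where it lasts more than 24 hours. Section 9, in its entry for the full local laboratory assessment, points to Section 10.1.1 for the analytes required. The visible biochemistry list there ends with "lactate dehydrogenase (LDH), C-reactive protein (CRP) and serum ferritin".

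SAP 6.4.1 plans a table, by system organ class and preferred term, of treatment-emergent events classified as DLTs, for the ITP only. Its visible text states no window. SAP 6.8 reports no departure from the methods in the protocol.

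**The concern.** A DLT is a time-limited event, so its definition is incomplete without one agreed end day. With two end days in force, two sites, or a site and the programming team, could classify the same Day 8 event differently and each be following the protocol.

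The label matters beyond a table. Protocol 12.4.1 names DLTs within the primary safety endpoint, and SAP 6.4.1 tabulates them. The synopsis ties reduction of the starting dose and two of its three visible stopping rules to a DLT. Section 6.3 lists a DLT among the reasons for removal from the study. Section 11 sends patients withdrawn early for a DLT into follow-up.

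The laboratory criteria raise a lesser question. A symptomatic event can be dated back when the patient is asked about adverse events at the next visit. A silent platelet or electrolyte abnormality first measured after the window closes cannot reliably be placed inside it. Section 3.5 treats severe thrombocytopenia as the foremost clinical risk, so it is worth confirming that the criteria, the panel and the schedule fit together.

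**Working it through.** The documents state no DLT rate, sample size or boundary, so there is no plan figure to reproduce. The check sets the texts side by side.

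**1. Window**

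| Source | Window | Length |
|---|---|---|
| Protocol synopsis | Days 1 to 7 | 7 days |
| Protocol 8.2.2 | Days 1 to 8 | 8 days |

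The longer window exceeds the shorter by 8/7 − 1 = 14%.

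**2. Classification of a qualifying event by onset day**

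| Onset | Synopsis | Section 8.2.2 |
|---|---|---|
| Days 1 to 7 | DLT | DLT |
| Day 8 | not a DLT | DLT |
| Day 9 or later | not a DLT | not a DLT |

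Only Day 8 onset is in dispute.

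**3. Is there a tie-breaker?** Section 8.2 names 8.2.2 as the place of definition, and the synopsis refers on to 8.2 for further detail. No visible text says that the body prevails over the synopsis. SAP 6.4.1 gives no visible window. SAP 6.8 carries the protocol's methods over unchanged, and with them the conflict.

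**4. Electrolyte criterion against the visible panel.** The biochemistry list in 10.1.1, counting urea or BUN once, is: creatinine, uric acid, urea/BUN, albumin, total bilirubin, GGT, ALP, ALT, AST, LDH, CRP and ferritin. That is 12 analytes, of which 0 are electrolytes. The other visible panels name none either.

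**5. Visible schedule against the window**

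- Hematology is due at every visit. The listed post-dose ITP days are 15, 29, 43, 57, 71, 85, 113, 141 and 169: 9 days, 0 of them on or before Day 8. The first comes 15 − 7 = 8 or 15 − 8 = 7 days after the window closes.
- Chemistry is monthly. The listed days are 29, 57, 85, 113, 141 and 169: 6 days, 0 of them on or before Day 8. The first comes 29 − 7 = 22 or 29 − 8 = 21 days after the window closes.

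**The case against.** **Section 8.2.2 governs.** The cross-references do point that way, and a careful site might settle on it. But the synopsis states a complete definition of its own with a different day, and nothing visible ranks the two. The contradiction stands.

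**The effect is small.** This is largely right. One onset day is in dispute, no visible text makes DLTs gate a cohort, and adverse event rates are not formally tested. It would be wrong to conclude that only reporting is affected, because the dose reduction, stopping and removal provisions refer to a DLT.

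**May against will is trivial.** It is minor, since the same safety condition applies in both places. It can be settled in the same clarification.

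**The laboratory points rest on redacted text.** This objection has force. The Schedule of Assessments, the ITP procedures and parts of Section 10.1 are not visible, so an in-window draw or an added analyte cannot be excluded. Section 11.2 also accepts clinically significant laboratory abnormalities as adverse events without limiting them to the listed panel, and unscheduled visits are allowed. What remains is a query, not a demonstrated defect.

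A reader might go further and infer that the DLT table cannot show how many patients were tested in the window, or that a zero count would be uninformative. The documents do not support this, because parts of SAP Section 5 and SAP 6.4.1 are redacted. Nor can a confidence limit for a zero count be usefully quoted. The number tested is not given, and patients tested at an investigator's discretion could not be assumed to represent everyone treated.

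**Conclusion.** The Day 7 and Day 8 definitions contradict each other in current, unredacted text and should be reconciled. The disagreement is confined to qualifying events that start on Day 8. How many patients that would be cannot be derived from the documents. It bears on the DLT part of the primary safety endpoint, the SAP table of DLTs, and the treatment provisions that depend on a DLT. The primary efficacy test and the sample size are unaffected. This conclusion needs no assumption beyond the two texts and the absence of a visible rule that ranks them.

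The electrolyte and schedule points are secondary and conditional. They hold for the visible panel and the visible visit days, and redacted text may answer them.

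**What to change.** - **Protocol.** The sponsor must reconcile the synopsis and Section 8.2.2 on the end of the DLT window and, as a minor matter, on whether downward dose adjustment *may* or *will* follow. This review takes no position on which is right.
- **SAP 6.4.1.** State the reconciled window beside the planned table of DLTs.
- **Check.** Confirm against the unredacted Section 10.1 and Schedule of Assessments that the electrolyte criterion, the laboratory panel and the sampling days agree.
- **Only if no in-window test is scheduled.** One sentence in SAP 6.4.1 could report, beside the DLT count, how many patients had a platelet result and how many had an electrolyte result inside the window, including unscheduled results. SAP 6.1.1.2 needs no edit, because it already allows exceptions stated in the analysis sections.

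The cost is a protocol clarification and one or two sentences in the SAP. If the check shows that the panel or schedule does not fit the criterion, the further cost depends on how the sponsor resolves it.

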9.1 Informed Consent

Patients must provide written informed consent before undergoing any study-related procedures. The Principal Investigator (PI), or designee, will explain to the patient the aims of the study, the risks and benefits involved and that their participation is voluntary. Each patient will acknowledge receipt of this information and that they wish to participate in the study by giving written informed consent for their involvement in the study in the presence of the PI, or designee, who will also sign and date the Participant Information Sheet/Consent Form (PISCF). Time, date, name of the person taking consent and any questions raised by the patient must be documented in the source data.

9.2 Screening Period, Including Enrollment

The Screening period is comprised of a Screening visit at which all assessments may be performed on the same day or multiple days, as needed, throughout the 28 day screening period. If the patient screen fails, document the reason(s) in the source data and on the Screening & Enrollment log.

Note for UK: AEs will be assessed at every visit. Non-serious events occurring pre-first IMG-7289 dose will be recorded as Medical History; those occurring post first IMG-7289 dose through the EoS visit will be recorded as AEs. Serious AEs (SAEs) will be recorded from time of consent through the EoS or until the Investigator and Imago determine that follow-up is no longer necessary.

9.2.1 Screening (Days -28 to Day -1)

- Review of all Inclusion and Exclusion Criteria
- Complete medical/medication history including:
 - 2016 WHO criteria for ET (Appendix 16.2).
 - Disease history (i.e., past bleeding episodes and thromboembolic events)
 - History of all treatments for their current disease (including clinical course with hydroxyurea and/or other ET therapy) or any previous oncologic conditions; including chemical, surgical and/or radiotherapeutic
 - All concomitant medication, in addition to any used in the 15 days prior to Screening
- Calculate ECOG Performance Status (Appendix 16.4)
- MPN-SAF, to be completed as close to Day -7 as possible. Additionally, provide patient with copy of the MPN-SAF for completion prior to dosing on Day 1. (Appendix 16.6)
- Full PE, including Vital Signs – review of all body systems as indicated by signs/symptoms
- Height (without shoes)
- Full Local Laboratory Assessment
- Coagulation
- Urinalysis
- **Note:** In Italy, HIV, HAV, HBsAg, HBsAb, HBcAb and HCV testing must also be performed.

CCI

9.2.2 Enrollment

For eligibility purposes, the following should be reviewed and/or confirmed:

- History of recent surgical procedures
- Recent use of investigational drugs
- Laboratory results, including historical laboratory values, will be assessed by the Principal Investigator (PI) before enrollment. Any deviation in laboratory values that are confirmed on re-examination to be clinically significant by the PI and that would jeopardize the safety of the patient or impact on the validity of the study results will result in exclusion of that patient.

Once Screening procedures have been performed and it is confirmed that the patient can be enrolled, patients will be enrolled in accordance with procedures detailed in the Study Reference Manual.

If the patient screen fails during this time, document the reason(s) in the patient's source data and on the Screening & Enrollment log.

9.2.3 Last Day of Screening Period (Day -1)

On Day -1, contact the patient and remind them to:

- Report to the clinic the following day at the agreed time

CCI

CCI

CCI

CCI

9.4 Additional Treatment Period (ATP)

Those patients deriving clinical benefit and safely tolerating IMG-7289; this definition applies throughout the document and will not be repeated with each reference to clinical benefit) that enter the Additional Treatment Period will 're-start' IMG-7289. For the purposes of clarity and efficiency, rather than continuing to present chronological days/weeks, visits are presented as 'ATP Day 1', followed by, 'ATP Days 29, 57, 85,' etc.

The visits and procedures contained herein may repeat as long as the patient continues to qualify for additional treatment. Continued treatment in the ATP should occur without interruption in dosing; Day 1 assessments may be performed on the same day as Day 169 of the prior treatment period.

Procedures are presented below for each visit by assessments performed pre-dose, at dosing, and post-dose (as applicable).

CCI

CCI

CC

CCI

CCI

Screening assessments and each study visit up to and including the EoS visit. Not included, however,

CCI [REDACTED]

[REDACTED]

[REDACTED]

[REDACTED]

[REDACTED]

[REDACTED]

[REDACTED]

[REDACTED] the particular analyte will only be analysed if the test is available at the particular institution.

